12.2. Reporting of AEs and SAEs

All adverse events will be recorded in appropriate adverse events case report form. The adverse events will be used for the safety assessment. An on-site visit to monitor the adverse event will be conducted if the principal investigator determines it is needed. These visits will be reported using designated case report forms. If during the last visit, an ongoing device-related AE is present, the participant will be monitored for approximately 2 weeks, until the AE resolves or a steady state is achieved.

The PI must report any SAE or SADE to the sponsor within 1 business day:

Theranica Bioelectronics [name]

[contact] Fax: [name]

Email: [contact]

The sponsor is responsible for reporting the adverse events to regulatory agencies, IRB/IECs, and investigators in accordance with all applicable global laws and regulations.

12.3. Anticipated device-related AEs

Possible adverse events associated with remote electrical neuromodulation include, but are not limited to, the following:

- Numbness of the hand/arm
- Itching
- Muscle spasms
- Redness
- Warmth sensation
- Tingling
- Pain in the arm

All anticipated devoice-related AEs, if present, are temporary and should disappear shortly after the treatment.

The following migraine symptoms are foreseeable and will not be considered as device related: headache, nausea, light sensitivity, sensitivity to noise, allodynia, abdominal pain,

Nerivio TCH-004 Clinical Study Protocol (NCT04089761)

Doc ID: TEC0105

Revision #: 1.0

Page: 45 of 49

loss of appetite, cold or heat sensation, paleness, fatigue, dizziness, anxious mood, fever (rare), blurred vision, vision symptoms such as bright flashing dots or lights, blind spots, wavy or jagged lines (aura).

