Informed consent and assent must be obtained from the parent/caregiver and participant, respectively, before any protocol-related activities are performed. Participants must be provided with a signed copy of the consent and assent forms. The eCRFs will be updated that informed consent and assent have been signed.

12. Adverse events

Adverse event (AE) is defined as any unfavorable and unintended medical change, temporally associated with the use of the sponsor's product, whether or not considered related to the use of the product. Any worsening (i.e., any clinically significant adverse

Nerivio TCH-004 Clinical Study Protocol (NCT04089761)

Doc ID: TEC0105

Revision #: 1.0

Page: 43 of 49

change in frequency and/or intensity) of a preexisting condition which is temporally associated with the use of the sponsor's product, is also an adverse experience. An adverse device effect (ADE) is an adverse event related to the use of the investigational device. In this study the ADE refers to side effect and complications.

A serious adverse event (SAE) is defined as an adverse event that leads to a) death,

- b) serious deterioration in the health of the subject, that either resulted in
 - 1) a life-threatening illness or injury, or
 - 2) a permanent impairment of a body structure or a body function, or
 - 3) in-patient or prolonged hospitalization, or
 - 4) medical or surgical intervention to prevent life-threatening illness or injury or permanent impairment to body structure or body function
- c) fetal distress, fetal death or a congenital abnormality or birth defect

A serious device related adverse effect (SADE) is an adverse event related to the use of the investigational device and that is considered by regulations and definitions as serious.

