12.1. Characteristics of AEs

An investigator who is a qualified physician, will evaluate all adverse events as to:

Maximum intensity

Mild: awareness of symptom, but easily tolerated Moderate: definitely acting like something is wrong

Severe: extremely distressed or unable to do usual activities

Duration

Record the start and stop dates of the adverse experience. If less than 1 day, indicate the appropriate length of time and units

Relationship of an AE and SAE to the study device

The relationship of the adverse event to the study device is defined as:

Definitely related: There is evidence of exposure to the device. The temporal sequence of the AE onset relative to use of the device is reasonable. The AE is more likely explained by the device than by another cause. Dechallenge is positive. Rechallenge (if feasible) is positive. The AE shows a pattern consistent with previous knowledge of the device.

Probably related: There is evidence of exposure to the device. The temporal sequence of the AE onset relative to use of the device is reasonable. The AE is more likely explained by the device than by another cause. Dechallenge (if performed) is positive.

Nerivio TCH-004 Clinical Study Protocol (NCT04089761)

Doc ID: TEC0105

Revision #: 1.0 Page: 44 of 49

Possibly related: There is evidence of exposure to the device. The temporal sequence of the AE onset relative to use of the device is reasonable. The AE could have been due to another equally or less likely cause. Dechallenge (if performed) is positive.

Definitely not related: The subject/patient did not use the device; or temporal sequence of the AE onset relative to device use is not reasonable; or there is another obvious cause of the AE.

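### Section 12.3 rules out a device relationship for listed migraine symptoms, section 12.1 has a physician judge it for every adverse event, and nothing says which label is used

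*Combined protocol and SAP*

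**What the plan says.** Section 12.1 opens: "An investigator who is a qualified physician, will evaluate all adverse events as to" intensity, duration and relationship to the device. Relationship is graded on four levels, from definitely related to definitely not related, using exposure, timing, alternative causes and dechallenge. Each of the three related grades requires, among other things: "The temporal sequence of the AE onset relative to use of the device is reasonable". The lowest of them, possibly related, covers this situation: "The AE could have been due to another equally or less likely cause". The not-related grade includes the case where "there is another obvious cause of the AE".

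Section 12.3 first lists anticipated device-related events, among them "Warmth sensation". It then says: "The following migraine symptoms are foreseeable and will not be considered as device related: headache, nausea, light sensitivity". The list continues with further symptoms, including "loss of appetite, cold or heat sensation, paleness, fatigue, dizziness, anxious mood, fever". The sentence carries no condition on onset, timing, worsening, seriousness or the investigator's opinion.

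Section 12 brings clinically significant worsening within the definition of an adverse event, where it is a worsening "of a preexisting condition which is temporally associated with the use" of the product.

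The device-relationship label is used in five places: primary endpoint 1 (sections 6.4.1 and 7.2.1), the device-related outputs of section 7.5.3, the safety data reviewed by the data monitoring committee (section 6.7), the two-week follow-up of device-related events still present at the last visit (section 12.2), and the study goal in section 5.1.

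**The concern.** One section asks for a judgement on each event. The other fixes the answer in advance for a group of events. Neither refers to the other, and the endpoint and analysis sections do not say which label they take.

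If 12.3 is applied literally, a listed symptom that the device may have caused is counted as unrelated. The effect runs one way, since 12.3 can remove events from the device-related count and cannot add any. It falls on part of a primary endpoint, in a single-arm study with no sham group to show how often these symptoms occur without the device. If sites read the two sections differently, the label will also mean different things at different sites.

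A smaller point lies within 12.3 itself. Warmth is an anticipated device effect, while a heat sensation is on the migraine list, and the text does not say how to tell them apart.

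**Working it through.** The plan states no figure on this point, so the check is mainly a comparison of the two rules.

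**1. Search for a rule of precedence.** The synopsis, sections 6.4.1, 7.2.1, 7.4, 7.5.1, 7.5.3, 9.1 and 9.3, and all of section 12 contain none.

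**2. Apply both rules to the same event.**

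| Event | Under 12.1 | Under 12.3 | Agree? |
|---|---|---|---|
| Nausea present before treatment, unchanged afterwards | Not related (the attack is an obvious cause) | Not related | Yes |
| Dizziness that begins during stimulation and settles when it stops; migraine no likelier a cause than the device | Possibly related or higher | Not related | No |
| Headache that worsens after stimulation by a clinically significant amount | Depends on whether the attack's own course is an obvious cause | Not related | Only if it is |

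The boundary is not perfectly sharp. Section 12.1 has no grade for a migraine cause that is likelier than the device but not obvious.

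**3. Direction.** Let R be the participants with at least one event rated related under 12.1, and R* those who remain when listed symptoms are relabelled as unrelated. R* is contained in R, so the count of R* is at most the count of R. The difference is the number of participants whose only device-related events are listed symptoms.

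**4. Size per participant.** Inputs: 110 and up to 130 participants (section 7.3), assuming all of them enter the ITT set.
- 1/110 = 0.91 percentage points
- 1/130 = 0.77 percentage points

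For scale, the adult pivotal study reports device-related events in 6/126 = 4.8% of its active group (section 4.2.2). How many adolescents would be relabelled cannot be derived from the documents.

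**5. Other information on cause.** The list has 15 items. Section 6.3 describes a baseline entry for each treated attack for 4 of them: headache pain, nausea, light sensitivity and noise sensitivity. Aura may also be captured, because section 7.5.4 allows a split by aura. That leaves 15 - 4 - 1 = 10: allodynia, abdominal pain, blurred vision and the seven items in "loss of appetite, cold or heat sensation, paleness, fatigue, dizziness, anxious mood, fever". Section 6.3 also plans an enrolment questionnaire on typical associated symptoms and a four-week diary. These give some information on what is usual for a participant, but the documents do not show that they cover the ten items. For these items the timing judgement in 12.1 is the only described assessment of cause at the level of the event.

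**The case against.** The best case for the plan is that 12.3 speaks of migraine symptoms, not of any event that shares a name with one. Read that way, it is a convention that applies the obvious-cause option of 12.1 in advance. This stands for symptoms that belong to the treated attack. It does not settle symptoms that start or worsen after stimulation, because 12.3 gives no test for belonging to the attack.

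It is also fair to say that nothing shows the 12.1 rating would go unrecorded. All adverse events are recorded (section 12.2) and tabulated by type (section 7.5.3), so a listed symptom recorded as an event stays visible. The case report forms and any separate analysis plan are kept outside the protocol (section 9.1) and may settle the matter. We have not seen them.

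Three stronger readings are tempting, and the documents support none of them.
- A reader might infer that 12.3 hides adverse events. It changes a label only.
- A reader might infer that the adult data show relabelling, or rule it out. In the adult study, 19 - 6 = 13 of 126 active and 15 - 3 = 12 of 126 sham participants had only events labelled unrelated. Those counts cover all event types, and the documents do not say whether this list was used there.
- A reader might infer that device warmth will be moved to the unrelated list. Warmth is named as an anticipated device effect, and the two lead-in phrases largely separate the lists. What remains is a missing distinction.

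**Conclusion.** The two sections conflict for listed symptoms that start or worsen after stimulation and have no other obvious cause. For those events the protocol does not determine the device-relationship label. If 12.3 is followed, the device-related count falls or stays the same.

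Affected: the device-relationship part of primary endpoint 1, the outputs in 7.5.3 on device-related events, device-related serious events and adverse device reactions, the device-related data seen by the monitoring committee, and the two-week follow-up. Not affected: overall incidence, events by type, seriousness, severity, non-completion because of adverse events, and the reporting of serious events to the sponsor.

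The size is unknown and may be small: 0.8 to 0.9 percentage points for each participant relabelled, assuming 130 to 110 participants in the ITT set. No numeric threshold or test depends on the rate, so the documents do not support saying that a pre-set study decision would change. The committee's judgement does draw on these data. The wording should be fixed because the possible error has a known direction, it touches a primary endpoint and it is cheap to remove.

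**What to change.** Reconcile 12.1 and 12.3. State that the 12.3 list is information on expected migraine symptoms, and that the investigator's rating under 12.1 is recorded for every adverse event, listed symptoms included, and supplies the label in sections 6.4.1, 7.2.1 and 7.5.3. In 7.5.3, tabulate device-related events with and without the listed symptoms. Ask the sponsor to say how warmth as a device effect is distinguished from the heat sensation on the migraine list. The documents give no body site for either, so that definition is for the sponsor to supply.

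The cost is some protocol wording, confirmation that the case report form captures the rating for listed symptoms, and one extra table. No new assessment is needed, because 12.1 already asks for the rating. The device-related rate may come out slightly higher, and sites may differ in how they attribute migraine symptoms. The two versions of the table would show how much of the rate comes from the listed symptoms.

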12.4. Device malfunction

Device malfunction is an inadequacy of the device with respect to its identity, quality, durability, reliability, safety, or performance, such as failure, use error or inadequate labeling. Device malfunctions may or may not be associated with an adverse event. All device malfunctions will be reported in the eCRF. Device malfunctions that were associated with an SAE or that could have led to an SAE if a) suitable action had not been taken or b) intervention had not been made or c) if circumstance had been less fortunate, will be reported within 24 hours of occurrence. If possible and needed, the device(s) associated with malfunction or failure will be retained until arrangements for its collection are made by the sponsor.

All device malfunctions will be summarized and reported in the clinical study report and will be reported to the regulatory authorities according to local reporting requirements.

13. Early termination

13.1. Criteria and procedures

The study may be discontinued if:

The sponsor decides to terminate the study due to company considerations (e.g. the data monitoring committee recommends terminating the study based on the interim analysis)

If in the opinion of study PI, the study presents an unreasonable medical risk to the patients, the PI may close the site under his/her responsibility.

If the clinical investigation terminated early or suspended, the sponsor will send a report justifying this decision to the corresponding IRB/EC, regulatory body and all investigators. A suspended or terminated clinical investigation may not be re-initiated without approval of the corresponding IRB/EC and relevant RA, as applicable. Enrolled subjects will be followed according to the institution's standards and guidelines.

13.2. Requirements for patient follow-up in case of withdrawal

If a patient withdraws consent, all efforts will be made to collect the final visit observations as soon as possible.

Nerivio TCH-004 Clinical Study Protocol (NCT04089761)

Doc ID: TEC0105
Revision #: 1.0

Page: 46 of 49

14. Publication policy

The publication policy is defined in the sponsor-investigator agreement.

15. Patient confidentiality & data protection

The privacy of the participants and the confidentiality of all personal data will be maintained in reports and publications and will not be otherwise published in any way. The privacy will be maintained according to prevailing national data protection, privacy and secrecy laws. Each patient will be identified by a unique patient identification number. However, the sponsor's monitor or representative and regulatory representatives, auditors and inspectors may have access to medical files in order to verify the authenticity of the data collected, as documented in the informed consent form.

16. Guidelines and applicable documents

- EN ISO 14155; (2011): Clinical investigation of medical devices for human patients
- EN ISO 14971; (2012): Medical devices Application of risk management to medical devices
- International Conference of Harmonization Good Clinical Practice guidelines
- FDA Guidance for Industry: Computerized Systems Used in Clinical Investigations

Nerivio TCH-004 Clinical Study Protocol (NCT04089761)

Doc ID: TEC0105

Revision #: 1.0

Page: 47 of 49

17. Reference

- 1. Vos T, AA Abajobir, KH Abate, C Abbafati, KM Abbas, F Abd-Allah, RS Abdulkader, AM Abdulle, TA Abebo and SF Abera (2017). Global, regional, and national incidence, prevalence, and years lived with disability for 328 diseases and injuries for 195 countries, 1990–2016: a systematic analysis for the Global Burden of Disease Study 2016. The Lancet 390: 1211–1259.
- 2. Society (IHS) HCC of the IH (2013). The international classification of headache disorders, (beta version). Cephalalgia 33: 629–808.
- 3. Abu-Arafeh I, S Razak, B Sivaraman and C Graham (2010). Prevalence of headache and migraine in children and adolescents: a systematic review of population-based studies. Dev Med Child Neurol 52: 1088–1097.
- 4. Stang PE and JT Osterhaus (1993). Impact of migraine in the United States: data from the National Health Interview Survey. Headache J Head Face Pain 33: 29–35.
